### **4.4.2 Assessment of New Lesions**

#### Assessment of new lesions

The occurrence of any new lesions (AK, NMSC such as BCC, SCC or Bowens disease and melanoma, according to AE page) will be summarized and tabulated according to SOC and PT displaying the number of events as well as counts and percentages on a subject basis. Additionally, the occurrence of any new lesions will be tabulated stratified by location in relation to the treatment field (inside - / in close proximity (< 10 cm distance to treatment field)).

### **4.4.3 Overall Tolerability**

#### Application site skin reactions during and post PDT

Details regarding application site skin reactions (erosion, erythema, exfoliation, oedema, fissure, induration, vesicles, ulceration, flaking, scabbing, discharge, other) will be listed.

#### Application site discomfort during and post PDT

Collected data about application site discomfort reported by the subjects for each category (Burning, Hyperaesthesia, Pain, Paraesthesia, Pruritus, Stinging, Warmth, other) will be listed.

#### Application site pain during PDT

Subjects will assess the maximum pain experienced during PDT using an 11-point Numeric Rating Scale (NRS-11) ranging from 0 (no pain at all) to 10 (worst possible pain). Basic statistics for application site pain will be given stratified by treatment area and overall.

Additionally, basic statistics for the NRS-11 score will be displayed stratified by concomitant medications given as pain relieving measures prior illumination (yes/no), concomitant medications given as pain relieving measures during illumination (yes/no) and physical measures taken during illumination (yes/no).

#### 4.4.4 Safety Assessments

##### Vital signs

The analyses of variables for vital signs will focus on

- A) the evaluation of the change from baseline (Visit 2, first measurement after the subject arrived at the site) to values on subsequent clinical visits and
- B) The evaluation of the change on Visit 2 from baseline (Visit 2, first measurement after the subject arrived at the site) to values obtained prior and after illumination (until 60 min post illumination).

Basic statistics of vital signs by visit / timepoint and of changes from baseline to post baseline visits as well as from Visit 2 baseline to values obtained prior and after illumination will be presented.

Boxplots per treatment area for Heart rate [beats/min], Systolic blood pressure [mmHg], Diastolic blood pressure [mmHg] and Body temperature [°C] on Visit 2 will be displayed stratified by measurement timepoint (at arrival / 10 min before start .... / 10 min after end ... / 60 (+/-10) min after end ...).

##### Safety laboratory

Information about clinically significant findings will be displayed using frequency tables. Details regarding laboratory sampling will be listed. In addition, a listing of subjects with clinically significant values will be provided.

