14 STATISTICAL PROCEDURES

14.1 General considerations

The principal features of the statistical analysis are described in this section. Technical details of the statistical analyses will be specified in a statistical analysis plan (SAP). The SAP will be finalized prior to the First-subject-first-visit for the final analysis of the study. The recommendations of the ICH E9 'Note for Guidance on Statistical Principles for Clinical Trials' including the addendum R1 to ICH E9 will be taken into account.

Unless otherwise stated, continuous data will be summarized by means of descriptive statistics, i.e. number of subjects, mean, standard deviation (SD), median, quartiles and range (minimum and maximum). Categorical variables will be summarized by absolute and relative frequencies (percentages) of subjects by category. Missing values will not be included in the calculation of percentages.

Eligible subjects who withdraw from study participation before IMP administration will be considered as dropouts.

The demographic data from screening failures and dropouts prior to IMP administration are entered into the clinical database and will not be passed through the data cleaning process. Their data are listed separately from data of treated subjects.

Statistical analyses will be conducted using SAS version 9.4 or higher (SAS Institute, 2010).

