14.4 Statistical methods

The planned analyses are of exploratory nature without any formal statistical hypotheses. All measured variables and derived parameters of subjects who are treated will be listed and, if appropriate, tabulated in summaries. For categorical variables, frequency counts and percentages will be used to summarize the results. Missing values will not be included in the calculation of percentages.

Descriptive statistics of continuous variables will be provided including number of observations, arithmetic mean, standard deviation (SD), median, quartiles as well as minimum and maximum.

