14.4.3 Evaluation of the Safety Endpoints

Safety analyses

All safety endpoints will be analyzed descriptively and in an exploratory way. These safety analyses will be performed for the safety set. Selected safety analyses will be conducted overall and stratified by age groups, sex, skin type, and treatment area.

AEs will be coded according to the latest Medical Dictionary for Regulatory Activities (MedDRA) version available at the day of database closure. The analysis will focus on the TEAEs. TEAEs will be summarized and tabulated according to primary system organ class and preferred term. TEAEs leading to death and TEAEs resulting in discontinuation of study will be tabulated using frequency tables.

The mean total duration of TEAEs including the breakdown of severity category (mild, moderate, severe) will be presented overall and by treatment area.

A listing of subjects with AEs will be provided for all subjects in the SAF.

The frequency of application site skin reactions and of application site discomfort will be presented overall, and per treatment area. The mean pain score (NRS-11) and the respective confidence intervals (CIs), and the range will be presented overall and by treatment area.

All laboratory values will be classified as normal or abnormal according to the laboratory's normal ranges and indicated as clinically significant or non-clinically significant by the investigator. Frequency tables for clinically significant findings will be provided. Laboratory values that are out of range and considered clinically significant will be additionally documented in the medical history (Visit 1) or as AEs (28 days after the PDT, Visit 5) and listed as such.

The analyses of variables for vital signs will focus on

- A) the evaluation of the change from baseline (Visit 2, first measurement after the subject arrived at the site) to values on subsequent clinical visits and
- B) The evaluation of the change on Visit 2 from baseline (first measurement after the subject arrived at the site) to values obtained prior and after illumination (until 60 min post illumination).

Descriptive analysis (number of subjects, mean, median and SD, minimum, maximum) of the time course and of changes from baseline to post baseline time points will be presented.

Physical examinations will include the following body systems: head, neck, skin, lymph nodes, thorax including heart and lung, abdomen, and musculoskeletal, peripheral vascular and nervous system.

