#### 4 Statistical Evaluation

Last assessment before administration of IMP will be used as baseline value. Change from baseline will be calculated as post-baseline value(s) – baseline value. If no baseline value is available, no change from baseline will be calculated.

No replacement of missing values will be done.

Unscheduled visits will only be listed and not included in any tables except table “Subjects per visit”. Data listings of laboratory assessments will present study days. The day of treatment will be identified as Study Day 1. The day before treatment will be identified as Day -1.

All analyses will be conducted by treatment area (face / scalp / face and scalp) and overall for the safety analysis set if not stated otherwise. Selected safety analyses will be conducted overall and stratified by age groups, sex, skin type, and treatment area.

Calculation of a duration in days (e.g. duration of AE [days]) is performed as follows: stop date - start date + 1 [day]. Details of calculation of AE duration by severity are specified in section 4.4.1: Duration and severity of AEs.

Duration of illumination [min] is calculated excluding interruptions. Calculation is performed as follows: stop time - start time - duration of interruptions. (Duration of interruptions will be set to 0 if illumination was not interrupted.)

All planned analyses are of exploratory nature without any formal statistical hypotheses.

A detailed description of the planned tables, listings and graphs is given in Appendix A (version 2.0).

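### Laboratory data are summarised only as investigator-flagged clinically significant findings; no specified table shows normal-range shifts or change from Visit 1 to Visit 5

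*SAP*

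**What the plan says.** SAP section 2 lists safety laboratory data as an endpoint in its own right, next to adverse events and vital signs. SAP 4.4.4 (Safety laboratory) then names three outputs. The first is the only table: "Information about clinically significant findings will be displayed using frequency tables". The other two are listings: "Details regarding laboratory sampling will be listed. In addition, a listing of subjects with clinically significant values will be provided".

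Protocol 14.4.3 asks for more at the data level: "All laboratory values will be classified as normal or abnormal according to" the laboratory's ranges. Each value is also to be "indicated as clinically significant or non-clinically significant by the investigator". For tabulation, however, it goes no further than the SAP: "Frequency tables for clinically significant findings will be provided".

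Two general statements cover listings. Protocol 14.4 says: "All measured variables and derived parameters of subjects who are treated will be listed and, if appropriate, tabulated in summaries". SAP section 4 says: "Data listings of laboratory assessments will present study days".

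**The concern.** The only laboratory summary that the plan commits to passes through a judgement made value by value at each site. That judgement sets a high bar: Protocol 11.1.1 illustrates a clinically significant result as one that prompts extra diagnostics, treatment or withdrawal. No numeric limits accompany it, and about 10 sites will apply it.

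A moderate movement across the group, or a cluster of values just outside range that each investigator regards as unimportant, need not trigger the flag in anyone. The planned table would then be empty for that parameter while the values had moved.

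The study exists to describe safety when three tubes are applied (468 mg ALA, Protocol 8.1.1), whereas the current label covers one tube (Protocol 4.2). With no control arm, the subject's own pre-treatment sample is the main reference available, and the specified tables do not use it.

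**Working it through.** The documents give no sample size, power or variance figure that bears on this point, so there is no figure of the plan to reproduce. The check sets the sections side by side.

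**1. What is collected.** Protocol 10.2.7 lists 13 chemistry, 10 hematology and 10 urinalysis parameters: 13 + 10 + 10 = 33. Table 1 schedules them at Visit 1 and Visit 5. For about 100 subjects that is 33 × 2 × 100 = 6,600 values, of which (13 + 10) × 2 × 100 = 4,600 are chemistry or hematology.

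**2. What is specified for reporting.**

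| Information | Listed | Tabulated in the SAP body |
|---|---|---|
| Clinically significant flag | Yes (SAP 4.4.4) | Yes (SAP 4.4.4) |
| Measured values | Foreseen (Protocol 14.4; SAP 4) | No |
| Normal/abnormal classification | Foreseen under the general rule in Protocol 14.4 | No |
| Change from Visit 1 to Visit 5 | Not named | No |

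**3. Whether the general rules fill the gap.** SAP section 4 defines baseline as the last assessment before IMP, and change as post-baseline minus baseline. No laboratory output is named that uses either definition. SAP 4.7 fixes the format of basic statistics but does not commit to producing them for laboratory data.

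**4. Comparison within the same SAP section.** Vital signs, also in 4.4.4, get basic statistics by visit and of change from baseline. Laboratory values get neither, and no reason is given. Protocol 14.4.3 shows the same contrast.

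**5. What the existing table adds.** Under Protocol 11.1.1 and 14.4.3, a clinically significant value found after screening is also recorded as an adverse event. It therefore already reaches the TEAE tables of SAP 4.4.1. The laboratory table largely repeats that information, and the unflagged measurements feed no summary.

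**6. Illustration (assumed numbers).** Let k of 100 subjects with both samples move from normal to above range on one parameter, and let f of those k be flagged, with 0 ≤ f ≤ k. For these subjects the planned table shows f/100 and a shift table shows k/100.

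- With k = 15 and f = 0: 0/100 = 0% against 15/100 = 15%.
- Over the full range f = 0 to 15, the planned table shows 0% to 15%, and the shift table shows 15% throughout.

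The value of k is not from the documents and is not a forecast. It only shows that the planned table measures flagging rather than movement.

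**The case against.** The strongest reply is that the two documents agree. Protocol 14.4.3 prescribes change from baseline for vital signs and frequency tables of significant findings for laboratory data, and the SAP carries that out. Clinically relevant laboratory changes also reach the TEAE tables, by SOC and PT, worst severity and relationship. The study is exploratory and has one sample before and one 28 ± 7 days after a single treatment, and fasting is not required. Extra tables would be hard to interpret and would alter no formal conclusion. All of this stands, and it limits how much weight the point can carry.

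Four stronger readings are tempting, and the documents do not support them:

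- *The measured values are discarded.* They are not. Protocol 14.4 and SAP section 4 both foresee listings. The values are missing from the specified summaries, not from reporting. Still, 6,600 listed values are a poor way to see a group movement.
- *The SAP breaches the default in Protocol 14.1 that "continuous data will be summarized by means of descriptive statistics".* That default yields wherever something else is specified, and Protocol 14.4.3 gives a laboratory-specific plan. The gap is common to both documents.
- *Baseline abnormality is not separated from new abnormality.* For clinically significant findings it is: Visit 1 findings go to medical history and Visit 5 findings to adverse events. Only for unflagged abnormal values does no specified table show the transition.
- *Open-label flagging biases the result.* Every subject receives the same treatment, so there is no between-arm comparison to distort. What matters is that the flag is a coarse, judgement-based filter, not that the investigator knows the treatment.

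Finally, SAP Appendix A holds the detailed output descriptions and is not in the public text. It may already contain laboratory summaries.

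**Conclusion.** The point holds as a gap in specification shared by SAP 4.4.4 and Protocol 14.4.3. As written, a shift in laboratory values that no investigator flags would appear in no specified table, although the endpoint is named and every value is to be classified against normal ranges. The size cannot be computed from the documents; the 0% against 15% contrast shows only the mechanism.

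This is a cheap improvement. It does not correct an error that threatens a conclusion. The verdict assumes that Appendix A adds no laboratory summaries, and that the measured values and reference ranges are held in the database, as the required classification implies.

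**What to change.** In SAP 4.4.4, alongside the table of clinically significant findings and unless Appendix A already provides them, add:

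- **Chemistry and hematology (23 parameters):** basic statistics by visit and of change from baseline to Visit 5, with baseline as the last value before IMP (as SAP section 4 defines it), plus a low/normal/high shift table from baseline to Visit 5.
- **Dipstick urinalysis (10 parameters):** a normal/abnormal shift table only. Mean changes and low/normal/high categories largely do not suit dipstick results.

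If Appendix A does contain these outputs, one sentence in 4.4.4 naming them is enough.

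No new data, visits or hypotheses are needed. The cost is programming and a few more descriptive tables. The SAP should state that, without a control arm, these tables cannot separate a treatment effect from ordinary variation, including variation from non-fasting samples.

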##### Physical examinations

Details of physical examination which involve head and neck, skin, lymph nodes, thorax including heart and lungs, abdomen, and musculoskeletal, peripheral vascular and nervous system status will be listed.

##### Neurological assessments

Neurological assessments comprise memory tests and neurological investigations.

Memory test results will be presented using frequency tables displaying whether all of the presented pictures were memorized correctly, and if not, the identified number of pictures, and which questions were answered correctly.

Information about neurological investigations will be presented using frequency tables showing results of assessment of clinical significance of pupils, coordination, gait and sensitivity. Information about clinically significant findings will be displayed using frequency tables.

#### 4.5 Missing Values

No missing value imputation method will be applied.

#### 4.6 Data Base Closure and Data Review

A data base closure will be performed prior to the analysis. All parameters will be checked, as specified in the data validation plan, and all queries resolved before data base closure and analysis.

SDTM datasets will be used to create ADaM datasets using ADaM Implementation Guide [REDACTED] and Analysis Data Model [REDACTED]. An ADaM specification document will be setup as a MS Excel spreadsheet, describing ADaM datasets to be created. A final define.xml [REDACTED] will be created when the ADaM datasets and the specification documents are final.

A data review will be conducted prior to data base lock based on all data to allocate the subjects to the analysis sets. Furthermore, the following items will be discussed:

- Any violation of inclusion/exclusion criteria
- Any dose changes/incompliance to study therapy
- Use of forbidden medication
- Premature discontinuation during the study
- Informed consent date not before application of IMP date or any other study related procedure

These evaluations and assessments will be done together and in agreement with the Sponsor, however, [REDACTED] will provide the Sponsor with the appropriate subject listings (as defined in appendix A). Data review can be done via a telephone conference. All protocol deviations detected during DRM will be listed.

#### 4.7 Miscellaneous

For qualitative variables the frequencies (absolute and relative) will be calculated. For frequency tables, the number of non-missing values will be presented. Missing values (including user-defined missing values) will not be presented and not included in the calculation of percentages. Percentages will be presented to one decimal place. Details of format of tables, listings and graphs are given in Appendix A, but the real design will be determined by the technical possibilities within SAS and may not look identical to the description. However, all information as mentioned will be included. Only observed outcomes will be displayed in frequency tables. If for a category no data is observed (e.g., females will not be displayed if all subjects are male) this category will not be displayed.

Quantitative parameters will be described by declaring the mean value, standard deviation, minimum, first quartile, median, third quartile, and maximum. In the description of the tables this will be denoted by „basic statistics“. In general, minimum and maximum will be presented to the same level of precision as the raw data; means and medians, standard deviation, and quartiles will be presented to one further decimal place.

The listings are always sorted by treatment area and subject. If a different sorting order should be used for some listings this will be remarked separately. The variables for the special listings are explicitly given in the description of listings. All listings will be presented for the safety analysis set, if not stated differently.

Screening failures and enrolled but not treated subjects (withdrawal before treatment) will be considered in tables and listings describing analysis sets, eligibility and discontinuation and separate demographic listings. Listings including screening failures and enrolled but not treated subjects will be stratified by SAF.

The following title will be used for all generated tables, listings, and graphs:

Protocol: ALA-AK-CT018  
Final Analysis

Page # of #

The numbering NNN of the tables/listings/graphs will be stated in the detailed description (Appendix A).

Following footnote will be used for all generated tables, listings, and graphs:

---

Program: <Name of program> Run date/time: yyyy-mm-ddThh:mm

All tables, listings, and graphs will be generated in A4 paper format.

The statistical evaluation will be performed using SAS version 9.4 or higher.

Signatures

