2 PROTOCOL OUTLINE

Title	
A non-randomized, open-label, multicenter study to evaluate the safety and tolerability of BF-200 ALA (Ameluz®) in the expanded field-directed treatment of actinic keratosis on the face and scalp with photodynamic therapy (PDT)	
Study no: ALA-AK-CT018	Clinical Phase: I
Study Design	
This is a non-randomized, open-label, multicenter study to evaluate the safety and tolerability of BF-200 ALA in the treatment of actinic keratosis (AK) located on the face and scalp with photodynamic therapy (PDT) when using the BF-RhodoLED® XL lamp. Each subject will receive the content of 3 tubes (6 g) of BF-200 ALA for an expanded field-directed treatment.	
Investigators / study sites	
Approximately 10 sites in the United States of America (US) will participate in this study. Each site should dose between 5 and 15 subjects. No site should dose more than 20 subjects unless prior approval of the sponsor is obtained. The maximum number should in no case exceed 25 subjects.	
Number of subjects	
It is planned to dose approximately 100 subjects.	
Subjects and lesions	
Subjects with mild to severe AK (according to Olsen et al., 1991) of all sexes and of age 18 years and older will be enrolled.	
Presence of at least 8 mild to moderate (Olsen et al., 1991) clinically confirmed AK lesions with a diameter \geq 4 mm within a treatment field on the face and/or scalp. In addition, severe AK lesions may be present in the treatment field. In case of severe AK lesions, a biopsy must be taken for confirmation of diagnosis. The treatment field may be continuous or in several patches, totaling about 60 cm ² in each subject and must be located within one effective illumination area.	
Definitions	

“illumination area” is the area effectively illuminated by one BF-RhodoLED® XL lamp in one illumination session“treatment field” is the part of the skin to which IMP is applied“treatment area” describes a region of the body in which the treatment field is located, distinguishing between face (including forehead, excluding eyes, nostrils, and mouth) and scalp (bald scalp, excluding ears)“target lesions” are all AK lesions (mild to severe) located within the treatment field	
Investigational products (IP)	
Investigational medicinal product (IMP)	

BF-200 ALA.

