This safety study is designed to confirm the safety and tolerability of BF-200 ALA (Ameluz[®]) in combination with BF-RhodoLED[®] XL for the field-directed treatment of mild to severe AK located on the face and scalp in an expanded treatment field of 60 cm², applying the content of 3 tubes of BF-200 ALA for PDT. Using the curved shape configuration of BF-RhodoLED XL permits an even illumination of the entire face or scalp and facilitates the illumination of discontinuous treatment field in one step.

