### 1.2 Study Objective

The objective of the study is to evaluate the safety and tolerability of BF-200 ALA PDT, utilizing BF-RhodoLED® XL illumination, in the treatment of mild to severe actinic keratosis on the face and scalp in an expanded field-directed treatment.

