### 1.3 Sample Size

In agreement with FDA about 100 subjects are considered sufficient to evaluate the safety profile after application of the content of 3 tubes of BF-200 ALA. All subjects will receive BF-200 ALA. No formal sample size calculation was conducted.

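### Adverse event rates are planned without intervals and unobserved categories get no row, so the report would not show what event rate about 100 subjects can exclude

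*SAP*

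**What the plan says.** **Purpose.** Protocol 4.2 states "This safety study is designed to confirm the safety and tolerability of BF-200 ALA", and Protocol 4.1 also speaks of confirming the safety profile. The formal objective is milder. SAP 1.2 has "The objective of the study is to evaluate the safety and tolerability of BF-200 ALA PDT", and Protocol 5.1 agrees.

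**Size.** SAP 1.3 states "In agreement with FDA about 100 subjects are considered sufficient to evaluate the safety profile" and adds "No formal sample size calculation was conducted". Protocol 7.1 and 14.7 say the same. Neither document gives a target precision or a rate to be excluded.

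**Analysis.** SAP 4 states "All planned analyses are of exploratory nature without any formal statistical hypotheses". For categorical data SAP 4.7 says "For qualitative variables the frequencies (absolute and relative) will be calculated". TEAEs by system organ class and preferred term, the overview table, adverse events of special interest (AESIs) and application site reactions (SAP 4.4.1) and new lesions (SAP 4.4.2) are all described as counts and proportions. SAP 4 splits the analyses by face, scalp, and face and scalp.

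**Display of zeros.** SAP 4.7 restricts frequency tables to outcomes that were seen; a category without data is left out.

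**Intervals.** The only interval in either document is for the mean NRS-11 pain score (Protocol 14.4.3, level not stated). SAP 4.4.3 plans basic statistics for that score, and SAP 4.7 defines these without an interval.

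**The concern.** A single-arm safety study has no comparator, so its conclusion rests on how precisely it estimates event rates. A count and a percentage do not show that precision, and a missing row shows nothing at all.

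This matters most for uncommon events. The plan looks for some of them: Protocol 9.1 treats past amnestic episodes as relevant history, Protocol 10.2.7 sets up memory testing to pick up a possible new one, and SAP 4.4.1 tabulates AESIs. If none occurs, the useful result is the upper limit on the rate. The planned tables would give neither that limit nor, under the display rule as worded, the zero itself. The gap widens in the treatment-area groups, where denominators are smaller.

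**Working it through.** There is no figure of the plan to reproduce: about 100 was set by agreement, without a calculation.

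**Inputs**
- n = about 100, all treated (SAP 1.3; Protocol 2: "It is planned to dose approximately 100 subjects").
- Three treatment-area groups (SAP 3.4 and 4). No group sizes are given.
- Assumed, because the documents give neither: a 95 % confidence level and the illustrative true rates p.

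**1. Zero events.** The exact two-sided 95 % upper limit is 1 − 0.025^(1/n).
- n = 100: 1 − 0.025^(1/100) = 3.62 %. The one-sided 95 % bound is 1 − 0.05^(1/100) = 2.95 %.
- Because n is approximate: 4.02 % at n = 90 and 3.30 % at n = 110.

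**2. Small counts in 100.** Clopper-Pearson limits are the 2.5 % quantile of Beta(x, n − x + 1) and the 97.5 % quantile of Beta(x + 1, n − x).

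| Events in 100 | Exact 95 % interval |
|---|---|
| 1 | 0.03 to 5.45 % |
| 2 | 0.24 to 7.04 % |
| 3 | 0.62 to 8.52 % |
| 5 | 1.64 to 11.28 % |

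**3. Chance of seeing at least one case.** This is 1 − (1 − p)^100.

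| True rate p | At least one case in 100 |
|---|---|
| 0.1 % | 9.5 % |
| 0.5 % | 39.4 % |
| 1 % | 63.4 % |
| 2 % | 86.7 % |
| 3 % | 95.2 % |

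A 1 % event is therefore missed with probability 0.99^100 = 36.6 %. Seeing at least one case with 95 % probability takes ln(0.05)/ln(1 − p) subjects, rounded up: 299 for p = 1 % and 99 for p = 3 %.

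**4. Treatment-area groups.** If 100 subjects fall into three groups, the smallest has at most 33, since 100/3 = 33.3. With zero events in 33, the upper limit is 1 − 0.025^(1/33) = 10.58 %, and a smaller group gives a higher limit. So 10.6 % is the best case for the smallest group, whatever the split. Purely as assumed sizes, the limit is 7.11 % for a group of 50 and 16.84 % for a group of 20.

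**The case against.** **The study claims no confirmation.** The objective is to evaluate, the analyses are declared exploratory, and *confirm* stands only in the introduction and rationale. This is right, and no success criterion is owed. But an interval is estimation and needs no hypothesis, and Protocol 14.4.3 already plans one for pain in the same exploratory study.

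**The size was handled openly.** Both documents say that no calculation was done and that the number was agreed with FDA. This stands; n is not in dispute here.

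**A reader can compute the interval from the count and the denominator.** This is true for a printed row. For a row left out, the reader must first know that the category was looked for.

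**Appendix A may specify intervals.** It was not available, so this cannot be excluded. The SAP's abbreviation list, which is meant to cover the outputs too, has no entry for confidence interval. That is weak evidence, because the list also omits NRS, which the SAP uses.

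**Stronger readings that the documents do not support**
- A reader might infer that zero counts will be taken as absence of risk. Neither document says so or sets any conclusion rule.
- A reader might expect zeros to be printed as 0.0 %. Under SAP 4.7 an unobserved category is not printed at all.
- A reader might expect severe local reactions to be rare. Protocol 4.3 points the other way: local reactions in 84-100 % of earlier subjects, and more severe ones on the face and scalp with 3 tubes on 60 cm².

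**Conclusion.** The point holds as a cheap improvement to reporting. In the text available, no adverse event rate has an interval, and the display rule in SAP 4.7 removes the rows where an upper limit would be most informative. Whether the sponsor would apply that rule to the fixed rows of the overview table is not stated; as worded, it makes no exception.

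The size of the gap is an upper limit of 3.6 % for zero events in 100, a 37 % chance of missing a 1 % event, and at least 10.6 % for zero events in the smallest treatment-area group. These figures rest on exact two-sided 95 % limits, n = 100 and binomial sampling of subjects. The 10.6 % needs no assumed split; the figures for groups of 50 and 20 do.

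The omission biases no estimate and alters no analysis set. A reader might want the rates set beside the sponsor's earlier 60 cm² study, but that study used a different lamp and the documents do not give its rates, so the point does not depend on it.

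A related inconsistency needs reconciling: the interval for mean pain in Protocol 14.4.3 is not carried into SAP 4.4.3.

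**What to change.** - **SAP 4.4.1:** add exact (Clopper-Pearson) 95 % intervals to the proportion of subjects affected for each overview-table row (including serious and related TEAEs), severe TEAEs, severe application site reactions and AESIs, overall and by treatment area. Apply them to subjects, not to event entries, because SAP 4.4.1 counts an event once for every treatment area it affects.
- **SAP 4.7:** exempt these prespecified rows from the rule that drops unobserved categories, so that a zero appears as 0/N with its upper limit. An interval option alone cannot put a limit on a row that is not printed.
- **SAP 1.3 and Protocol 7.1/14.7:** state what n = 100 delivers. For example: with no event in 100 subjects the exact 95 % upper limit is 3.6 %, and an event with a true rate of 3 % would be seen at least once with 95 % probability.
- **Protocol 4.1 and 4.2:** align *confirm* with the objective's *evaluate*.
- **SAP 4.4.3:** add the interval for mean NRS-11 promised in Protocol 14.4.3, and state its level.

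Cost: SAP and protocol wording, minor table programming and no new data. The reported safety results will look slightly less favourable. If Appendix A already contains such intervals, the SAP body need only refer to them; the zero-row exemption should still be checked.
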